In Malawi, all pregnant women presenting for care receive opt-out HIV testing at their first antenatal care visit. Women who test HIV+ undergo adherence counseling and start ART the same day. PND screening and assessment are rare to nonexistent at antenatal/ART clinics in Lilongwe, as in most clinical settings in Malawi.

UNC Project in Lilongwe will serve as the administrative home for the study and has longstanding relationships with Bwaila FHU, antenatal/ART clinics in Lilongwe, and the Ministry of Health.

F4. Study Population:

Women (92 total): As of this protocol v3.2, we have recruited a total of 12 women from our original 3 clinics. As we launch activities at our two new clinics and reduce to 2 arms, we will seek to recruit 40 new participants per arm or 80 new participants total, for a total enrollment of 92 participants. All 92 women will contribute to analyses of feasibility and acceptability, but only the new 80 women will contribute to between-arm comparisons due to the differences in sites.

We will include 92 HIV-infected, depressed women initiating, re-initiating, or continuing ART who engage in ANC and are identified with antenatal depression at ≤ 34 weeks gestation to allow sufficient time for approximately 4 prenatal counseling sessions and approximately 2 postnatal counseling sessions. Women with a score ≥ 10 on the EPDS^{48,49} and/or ≥ 8 on the SRQ-20 will be considered to be depressed and will be invited to participate.

Inclusion criteria:

- HIV-infected, pregnant women initiating, re-initiating, or continuing ART during antenatal care (ANC)
- ≤ 34 weeks gestation to allow sufficient time for approximately 4 prenatal counseling sessions and approximately 2 postnatal counseling sessions.

- Screened positive for depression with a score ≥ 8 on the SRQ-20
- At least 18 years of age

Feasibility of recruitment – Approximately 30 HIV-infected women initiate or re-initiate ART monthly at each of the study sites, or 150 women over 6 months, with ~90% presenting at ≤ 30 weeks. Based on our group's systematic review³⁴, we conservatively estimate 30% of HIV-infected women will have antenatal depression, suggesting that enrolling ~6 women per site per month is feasible. Utilization of two additional clinics will aid in timely participant recruitment should enrollment at the three primary sites lag behind expected targets.

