6-month Postpartum Visit: At 6 months postpartum, HIV-infected women will be asked to complete the EPDS and SRQ-20 either in-person or by phone. Viral load measures for all HIV-infected women will be collected by study personnel at 6 months postpartum. Information on HIV appointment attendance and infant HIV testing during the first 6 months postpartum will be collected from a participant's medical record, as we are doing in our ongoing USAID project. Information on infant anthropometry (length, weight, head circumference), infant physical health (presence of respiratory illness, diarrhea, and immunization records) and infant development, assessed using the Observation of Mother-Child Interaction (OMCI) guide, the PAMANED Study Family Care Indicators Questionnaire in Chichewa, and the WHO Indicators of Infant and Young Child Development (IYCD) Item guide, which have been validated for use in children as young as 4 months of age, will also be collected (Appendix 2). The OCMI portion of the 6 month postpartum visit will be video-recorded to review the fidelity rating after the visit has occurred. HIV-infected women, counselors and supervisors will be asked to complete a brief exit interview either in-person or by phone to assess the feasibility and acceptability of the intervention.

Counseling Sessions (EFB n= up to 7; ESC, n=0):

Women will be followed from study enrollment at their ANC visit through 6 months postpartum. Women in the

AFB and EFB arms will receive approximately 4 prenatal individual counseling sessions and approximately 2 optional, but recommended postnatal group counseling sessions (n=up to 6 counseling session). Women in the EFB arm will receive up to the same number of counseling sessions (4 prenatal and 2 postnatal) as women in the AFB arm, with an additional social support session described in section F6 (n=up to 7 counseling sessions). Women in the ESC arm will not receive counseling sessions, but will receive psychoeducation from a trained research assistant, referrals as needed, and follow-up calls to assess whether referrals were acted on and whether any further unmet mental health needs remain (n=0 counseling sessions). Counseling sessions will take place every 1-2 weeks at the antenatal care clinic, or via phone, during the prenatal period and approximately monthly during the postnatal period to coincide with routine ART refill visits.

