Data Collection: At each counseling session (prenatal and postnatal) women will be asked to complete the EPDS and SRQ-20 to assess their mental health status.

F9. Outcomes – The primary goal of this R34 application is to evaluate the feasibility, acceptability, and fidelity of a counseling intervention to improve PND and engagement in HIV care among HIV-infected women. Recognizing the small sample size, indicators of preliminary effectiveness of the intervention for mental health and engagement in care outcomes will be reported as secondary outcomes. Primary and secondary outcomes will be assessed at 6 months postpartum and compared across the study arms.

F9.a. Primary Outcomes:

Feasibility will be defined as the ability to successfully enroll and retain HIV-infected, depressed women in the pilot intervention. Feasibility will be assessed as the number of women enrolled, a comparison of planned to actual enrollment and reasons for non-enrollment, and the proportion of women retained in each arm at 6 months postpartum.

Acceptability will be defined as the ability to deliver a culturally and resource-appropriate intervention. Acceptability will be assessed through brief exit interviews among a subset of HIV-infected women. Exit interviews will include both closed and open-ended questions and will assess how easy the intervention was to participate in or deliver, the perceived usefulness of the intervention, and suggestions for improvement.

Fidelity will be defined as adherence to the intervention protocol. Fidelity to session content for both individual and group counseling sessions will be assessed by members of the Friendship Bench team (DHO or study psychiatrist), by using a checklist of intervention characteristics either during direct monitoring or using audio recording of up to 3 randomly chosen sessions per counselors. Scoring either 'meeting expectations' or 'exceeding' expectations' on at least 80% of applicable checklist items during each session will be considered fidelity to the intervention protocol.

F9.b. Secondary Outcomes: Secondary outcomes will be used to provide preliminary information about effectiveness at 6 months postpartum, taking into consideration the limited sample size for the pilot project.

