F11. Sample Size. The primary goal of this R34 proposal is to evaluate the feasibility, acceptability, and fidelity of the adapted and enhanced Friendship Bench intervention to improve PND and engagement in HIV care among HIV-infected women. In Aim 3, we will enroll 92 HIV-infected women with PND in a 2-arm pilot (n=12 total in the clinic-randomized phase, n=40 women per arm in the individually randomized phase) to compare enhanced standard care with the enhanced Friendship Bench intervention. Information on preliminary effectiveness of the intervention across a range of mental health and engagement in HIV care outcomes will be assessed, but interpreted cautiously as effectiveness is not the primary aim of this pilot study. Intervention effectiveness will subsequently be assessed in a large-scale clinic-randomized controlled trial. Given that the objective of this analysis is to estimate feasibility, acceptability, and fidelity of the described interventions, feasible sample sizes (n=40/arm; 92 including both the clinic-randomized and individually randomized phases) were determined according to clinic patient volumes and estimated perinatal depression among women living with HIV in the study setting. Precision estimates for the given sample size are based on two-tailed statistical significance tests and a Type 1 error probability (α) of 0.05. The sample of 92 women (40 per arm) will be sufficient to estimate quantitative measures of feasibility and acceptability with reasonable precision (e.g., confidence intervals around proportions of ± 5 -9 percentage points across all arms, and ± 9 -17 percentage points within a given arm). This margin of error was estimated using a desired sample size of 92 and population feasibility and acceptability proportions ranging from 10 to 50%.

E. Potential Challenges and Solutions

What if women are lost to follow-up (LTFU) between pre and postnatal care? Our proposal directly addresses the high rate of LTFU in the postnatal period^{2,52} for women on Option B+ by providing linkage to care coordination from the antenatal to ART clinic and measuring engagement in care through 6 months postpartum. The information gathered at the pilot stage will help to inform the design of a large-scale randomized controlled trial to improve PND and engagement in HIV care during the peripartum period.

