Baseline Visit: At the baseline visit, women will be asked to fill out a questionnaire about their mental health, HIV, and reproductive health history. In addition to assessing depression with the EPDS, we will assess the prevalence of common mental disorders using the Self-Reporting Questionnaire (SRQ-20). The SRQ-20 was designed by the World Health Organization as a screening tool for common mental health disorders (CMD). The SRQ-20 has 20 questions exploring symptoms of depression, anxiety and somatic complaints, rather than a specific diagnosis of depression or anxiety. The SRQ-20 was validated in Malawi and is available in Chichewa.^{50,51} A cut-point of 8 or above has been previously used in Malawi to identify probable CMD. The baseline interview will also assess socio-demographics, self-reported health, and key structural and psychosocial factors including trauma history, intimate partner violence (IPV), other violence in the home, socioeconomic measures, coping, social support, self-efficacy, and experiences of stigma related to HIV and mental health (Appendix 2). Measures of trauma, IPV, and other violence will be important for understanding participants' experience of depression in their broader socioecological context. We have used these measures previously in similar settings.

6-month Postpartum Visit: At 6 months postpartum, HIV-infected women will be asked to complete the EPDS and SRQ-20, either in person or by phone. Viral load measures for all HIV-infected women will be collected by study personnel at 6 months postpartum. Information on HIV appointment attendance, infant birthweight, and infant HIV testing during the first 6 months postpartum will be collected from a participant's medical record, as we are doing in our ongoing USAID project. Information on infant anthropometry (length, weight, head circumference), infant physical health (presence of respiratory illness, diarrhea, and immunization records) and infant development, assessed using the Observation of Mother-Child Interaction guide, the PAMANED Study Family Care Indicators Questionnaire in Chichewa, and the WHO Indicators of Infant and Young Child Development (IYCD) Item guide, which have been validated for use in children as young as 4 months of age, will also be collected (Appendix 2). HIV-infected women, counselors and supervisors will be asked to complete a brief exit interview, either in person or by phone, to assess the feasibility and acceptability of the intervention.

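### Acceptability, a primary outcome, is measured in an unspecified subset of women (F9.a), but its analysis and precision assume all 92 (F4, F11)

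*Combined protocol and SAP*

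**What the plan says.** The combined protocol and SAP describes who is assessed for acceptability in five places.

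- F9.a (Primary Outcomes) limits it: "Acceptability will be assessed through brief exit interviews among a subset of HIV-infected women". It adds that these interviews hold both closed and open-ended questions. No other acceptability instrument is described.
- F4 (Study Population) says "All 92 women will contribute to analyses of feasibility and acceptability". Only the 80 newly recruited women enter between-arm comparisons.
- F8 (6-month Postpartum Visit) says "HIV-infected women, counselors and supervisors will be asked to complete a brief exit interview either in-person or by phone". It names no subset and gives no number.
- Section J (Sources of Materials) repeats that step, again without a subset.
- F11 (Sample Size) says "The sample of 92 women (40 per arm) will be sufficient to estimate quantitative measures of feasibility and acceptability with reasonable precision". It gives "confidence intervals around proportions of ± 5 -9 percentage points across all arms", and a range of 9 to "17 percentage points within a given arm". These are for proportions of 10% to 50% and a two-sided 0.05 level.

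F10 then reports acceptability as a proportion of participants. F9 sets the primary outcomes at 6 months postpartum. No exit interview at withdrawal is described, and no rule is given for missing exit interviews.

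**The concern.** F9.a defines the outcome, so it is the section that study staff would follow. Read literally, it allows a few women to be interviewed, chosen by no stated rule, while F4 and F11 tell the reader that the figure describes all 92. The two cannot both be carried out.

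Acceptability is one of three primary outcomes, and the pilot is meant to support a later randomised trial. A proportion with no defined denominator, and with less precision than was stated, is weak support for that step. Because the interview takes place only at about 6 months postpartum, women lost to the study before then would also be absent from the figure, and the plan does not say how that would be shown.

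**Working it through.** **Inputs.** From F11: n = 92 overall, 40 per arm, proportions p from 10% to 50%, two-sided 0.05 (z = 1.96). The arm and phase sizes agree with the total: 12 + 2 × 40 = 92. The documents give no subset size and no allowance for study dropout, so every n below 40 is an assumption.

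**Formula.** Wald 95% half-width = 1.96 × √(p(1 − p)/n).

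**The plan's own figures.**
- Overall, n = 92: 1.96 × √(0.09/92) = 6.1 points at p = 10%, and 1.96 × √(0.25/92) = 10.2 points at p = 50%. F11 states 5 to 9.
- Within an arm, n = 40: 9.3 points at p = 10% and 15.5 at p = 50%. F11 states 9 to 17.
- A half-width of 9 points at p = 50% needs 0.25 × 1.96²/0.09² = 118.6, so 119 women.

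Wilson, Clopper-Pearson and continuity-corrected intervals do not reproduce both stated ranges either. The superseded design (105 women, 35 per arm) gives 5.7 to 9.6 and 9.9 to 16.6. That is closer, but it matches only with mixed truncation and rounding. The ranges may have been carried over, though the documents do not say so.

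**If fewer women are interviewed.**

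| Women interviewed | Half-width, p = 10% | Half-width, p = 50% |
|---|---|---|
| 40 in an arm | 9.3 | 15.5 |
| 34 | 10.1 | 16.8 |
| 33 | 10.2 | 17.1 |
| 28 | 11.1 | 18.5 |
| 20 | 13.1 | 21.9 |
| 10 | 18.6 | 31.0 |

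The break-even for 17 points at p = 50% is 0.25 × 1.96²/0.17² = 33.2. With fewer than 34 women interviewed in an arm, the half-width exceeds the stated upper limit.

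**What missing interviews could do.** As an illustration only, assume that 70% of women are interviewed and 90% of those are favourable. If none of the others were favourable, the figure among all women would be 0.7 × 0.9 = 63%. If all of them were, it would be 63% + 30% = 93%. The observed 90% lies inside that range, and nothing in the plan narrows it.

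**The case against.** The strongest reply is that the sections can be reconciled. The F4 sentence mainly sorts the two recruitment phases into analyses: 92 pooled, 80 between arms. F8 does not say that all women are interviewed, although the same paragraph does say so for viral load. A subset could be meant for qualitative work only. The first two observations are fair, and F8 should not be read as promising 92 interviews. The third fails, because F9.a puts the closed questions in the subset interview and no other source exists for the F10 proportion. F11 also remains, and it rests acceptability precision explicitly on 92 women.

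A second reply is that the loss of precision depends on assumed subset sizes. That is true. With 34 women in an arm the stated 17 points is still met at p = 50%. At p = 90%, which has the same half-width as 10%, 20 women give 13.1 points. That is still wider than the 9.3 points that 40 women give.

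A reader might go further and infer that women who disengage are never asked, that staff pick whom to interview, or that the result is biased upward by a known amount. The documents support none of these.
- Interviews may be by phone and follow-up runs to 6 months postpartum, so a woman who stops counseling or HIV care can still be interviewed. Only women lost to the study are missed, and retention by arm is itself reported.
- No selection rule is stated, which is not the same as selection by staff.
- The background figure of up to 30% lost concerns HIV care within 6 months of starting ART. It is not study dropout at 6 months postpartum, and women continuing ART are also eligible.

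**Conclusion.** The inconsistency between F9.a and both F4 and F11 is real and concerns a primary outcome. Followed as written, F9.a leaves the F10 proportion without a defined denominator and the F11 precision without a basis. How much precision is lost depends on a subset size that the plan does not give: none beyond the stated 17 points if at least 34 women in an arm are interviewed, and about 22 points at p = 50% if only 20 are. Separately, the overall range in F11 is too narrow even with all 92 women interviewed (6.1 to 10.2 points against 5 to 9).

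Selective measurement is possible because nothing is provided for women lost before the 6-month interview. Any statement of its size or direction would rest on assumed dropout and assumed views, so the point stops at the missing provision.

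**What to change.** - In F9.a, remove the restriction to a subset for the closed acceptability items. Give them to every woman contacted at the 6-month interview, in person or by phone as F8 already allows. Open-ended questions can stay with a subset.
- Report acceptability among women interviewed, by arm. Show beside it the number allocated and the number not reached, with best-case and worst-case bounds for those not reached. Dividing by all women allocated would count unreached women as unfavourable, so that figure should appear only as the lower bound.
- Restate the F11 half-widths for the number of women expected to be interviewed.
- If the sponsor keeps a subset, state its size, random selection and arm split, and correct F4 and F11 to match.

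A short call when a woman stops sessions early would be an optional design addition and is not needed to remove the inconsistency.

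The cost is a change of wording, a few minutes at a contact that is already planned, and a stated precision that may look less favourable.

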PND may be a barrier to the success of Option B+, the rapidly expanding effort to initiate all HIV-infected pregnant women on lifelong ART.^{39,40} Option B+ is expected to have major benefits by preventing vertical HIV transmission, improving maternal health, and reducing onward sexual transmission. However, the realization of these benefits requires engagement in HIV care, which has emerged as a major challenge and priority area of research for the National Institute of Mental Health (NIMH). In Malawi, up to 30% of women are lost to HIV care within 6 months of starting ART^{2,41} and globally just 28% of HIV-exposed infants are tested for HIV within 2 months of birth.^{42,43} Given the strong and consistent associations between depression and HIV outcomes in general (non-pregnant) HIV-infected populations¹⁴⁻²⁰, women with the dual burden of HIV and PND may be at particularly high risk for disengagement from HIV care.⁴⁴

Evidence-based PND interventions exist, but they have not been adapted to the unique needs of HIV-infected women. We proposed to adapt The Friendship Bench, an evidence and theory-based counseling intervention that improves depression in the general population.^{24,45} Friendship Bench uses problem-solving therapy^{46,47} to help participants identify a problem they can address, such as barriers to attending their HIV visits, during counseling sessions with trained, supervised lay healthcare workers. The Friendship Bench has been adapted to address PND among postpartum women³², but has not been adapted to the specific needs of HIV-infected women. HIV-infected women with PND face unique issues surrounding disclosure to their partner, stigma related to HIV and PND, concerns over perinatal HIV transmission, and barriers to ART adherence and retention in HIV care. For these reasons, PND among HIV-infected women may lead to suboptimal engagement in HIV care. Addressing these issues through evidence-based interventions is essential to address NIMH's research priorities of supporting engagement in HIV care and improving HIV care outcomes.

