Composite outcome: Retained in HIV care, with improved depression: We will assess a combined outcome at 6 months of whether a woman attended an HIV visit within the last 30 days and achieved remission (defined as ≥50% improvement in SRQ-20 score from baseline and an SRQ score <8). We will compare the following additional outcomes at 6 months postpartum: Self-Reporting Questionnaire (SRQ-20): The proportion of women reporting a score >8; Retention in HIV Care: (a) The proportion of women who attended an HIV care visit in the last 30 days; (b) considering the increase in visit spacing during the COVID-19 pandemic, we will consider a second definition of retention in HIV care of at least 2 visits at least 30 days apart in the first 6 months postpartum; Viral Load Suppression: The proportion of women with a HIV RNA level <1000 copies/mL; Infant health: the proportion of women whose infants received an HIV RNA test.

F10. Statistical Analysis – Baseline mental health, HIV, and reproductive health characteristics of women will be compared across 2 study arms using t-tests for continuous variables and chi-square tests for categorical variables to assess balance across study arms. **Primary Outcomes** – Quantitative measures of feasibility, acceptability, and fidelity will be summarized using means and standard deviations or proportions and compared across arms using statistical models for continuous or binary outcomes, as appropriate. Specifically,

we will compare the mean number of women enrolled and the proportion of women retained in EFB or ESC through 6 months postpartum (feasibility); the proportion of participants who found the intervention easy to administer and helpful (acceptability), and the proportion of counseling sessions scoring either 'meeting expectations' or 'exceeding' expectations' on at least 80% of applicable checklist items (fidelity) across study arms. **Secondary Outcomes** will be analyzed as above at 6 months postpartum across 2 study arms. In addition, statistical models examining differences in SRQ-20 scores at 6 months will be generalized linear models.

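### F10 gives no denominator or missing-data rule for the 6-month composite and SRQ-20, so women already known to have failed retention could be dropped; the SRQ-20 model also names no baseline adjustment

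*Combined protocol and SAP*

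**What the plan says.** F9.b sets the composite as "a combined outcome at 6 months of whether a woman attended an HIV visit within the last 30 days and achieved remission", with remission "defined as ≥50% improvement in SRQ-20 score from baseline and an SRQ score <8". Both parts are needed for success.

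The two parts have different sources. In F8, at the 6-month postpartum visit, women are asked to "complete the EPDS and SRQ-20 either in-person or by phone", whereas "Information on HIV appointment attendance and infant HIV testing during the first 6 months postpartum will be collected from a participant's medical record".

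F10 says that secondary outcomes "will be analyzed as above at 6 months postpartum across 2 study arms" and that "statistical models examining differences in SRQ-20 scores at 6 months will be generalized linear models". It names no covariate, analysis set, missing-data rule or sensitivity analysis. F4 restricts between-arm comparisons to the 80 newly recruited women, but does not say how a woman without a 6-month score is counted.

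The plan expects disengagement. The literature review (D) states that in Malawi "up to 30% of women are lost to HIV care within 6 months of starting" ART. The section on potential challenges asks "What if women are lost to follow-up (LTFU) between pre and postnatal care" and answers with linkage to care and measurement of engagement, not with an analysis rule.

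**The concern.** The composite joins a component that can be read from the record for each woman to one that needs an interview. By the definition, a woman with no recorded visit in the last 30 days has failed, with or without an SRQ-20. A dataset that builds the composite from both variables will nonetheless set it to missing when SRQ-20 is missing, unless a rule prevents this. A GLM fitted to the SRQ-20 score will likewise omit women with no score.

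This could differ by arm. F6 gives EFB a social-support session and up to six home visits, and gives ESC up to three follow-up contacts. If disengaged women are harder to interview, dropping them removes known failures, and removes more of them from the arm with poorer retention. The composite is the outcome meant to capture retention and mental health together, and its estimate will inform the larger trial.

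Separately, SRQ-20 is measured at baseline in every woman, yet F10 does not say that the 6-month model uses it. With 40 women per arm, that gives up precision that costs nothing to obtain.

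**Working it through.** **Plan's own figure.** There is none on this point: no dropout rate, power or precision is given for the composite or SRQ-20. F11's only numbers are half-widths for feasibility and acceptability proportions, and they do not enter here.

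**Inputs from the documents.** Composite = visit and remission (F9.b). Attendance from the record, SRQ-20 from the interview (F8). 40 women per arm in the between-arm comparison (F4, F11).

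**Assumed inputs, not in the documents.** Retained in care R: 85% EFB, 70% ESC. Remission among retained women m: 50% in both arms. SRQ-20 obtained in 95% of retained women and in a share q of disengaged women, with q = 20% as the main case.

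**Formulas.**
- True composite = R × m.
- Composite missing whenever SRQ-20 is missing = 0.95·R·m / (0.95·R + q·(1 − R)).
- Record rule (no recorded visit = failure; retained women without SRQ-20 left out) = 0.95·R·m / (0.95·R + (1 − R)).

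**Main case.**
- True: EFB 0.85 × 0.5 = 42.5%; ESC 0.70 × 0.5 = 35.0%; difference 7.5 points.
- Missing if SRQ-20 missing: EFB 0.40375 / (0.8075 + 0.03) = 48.2%; ESC 0.3325 / (0.665 + 0.06) = 45.9%; difference 2.3 points.
- Record rule: EFB 0.40375 / 0.9575 = 42.2%; ESC 0.3325 / 0.965 = 34.5%; difference 7.7 points.

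**Range over q** (true difference 7.5 points throughout):

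| SRQ-20 obtained in disengaged women | EFB | ESC | Difference (points) |
|---|---|---|---|
| 0% | 50.0% | 50.0% | 0.0 |
| 20% | 48.2% | 45.9% | 2.3 |
| 40% | 46.5% | 42.4% | 4.2 |
| 60% | 45.0% | 39.3% | 5.6 |
| 80% | 43.5% | 36.7% | 6.8 |
| 95% (same as retained) | 42.5% | 35.0% | 7.5 |

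**If EFB also improves remission** (60% vs 50%, q = 20%):
- Retention 85% vs 70%: true 51.0 − 35.0 = 16.0 points. Missing if SRQ-20 missing: 0.4845 / 0.8375 − 0.3325 / 0.725 = 57.9 − 45.9 = 12.0 points.
- Retention 70% in both arms: true 42.0 − 35.0 = 7.0 points. Missing if SRQ-20 missing: 0.399 / 0.725 − 0.3325 / 0.725 = 55.0 − 45.9 = 9.2 points (before rounding). Here the difference grows.

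So rates are overstated whenever disengaged women are interviewed less often. The difference shrinks when the EFB effect runs largely through retention.

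**SRQ-20 alone.** For a proportion with k of 40 scores missing per arm, the best-to-worst-case range of the difference is 2k/40: 20, 40 or 60 points for k = 4, 8 or 12 (10%, 20%, 30% missing). The documents give nothing that fixes the direction.

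**Scoring every missing SRQ-20 as failure.** Assume 80% retained and 50% remission in both arms, with retained women interviewed in 95% (EFB) and 80% (ESC). The rates become 0.80 × 0.95 × 0.5 = 38% and 0.80 × 0.80 × 0.5 = 32%, so a true difference of 0 appears as 6 points.

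**Baseline adjustment.** With a linear model, adjustment multiplies the residual variance by about 1 − r², where r is the baseline-to-6-month correlation. The documents give no r, so the gain is not sized here.

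**The case against.** A reader might infer that the plan analyses these outcomes only in interview completers and that the comparison is therefore biased. The documents do not support that. F10 is silent; it does not prescribe complete-case analysis. Read literally, the composite's definition already makes a woman with no recorded visit a failure, so only retained women without an SRQ-20 are undetermined.

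Nor can the cited 30% be read as expected missing interviews. It is loss from HIV care after starting ART, the trial also enrols women continuing ART, and a woman out of care can still be interviewed by phone. No study dropout rate is given.

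The 5.2-point shift (7.5 − 2.3) is also small beside the sampling error. The 95% half-width for the difference is 1.96 × √(0.425 × 0.575/40 + 0.35 × 0.65/40), about ±21 points. A retention effect would not be hidden either, because F9.b reports retention in HIV care separately and F9.a reports the proportion retained per arm. F11 asks for cautious interpretation of effectiveness.

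All of this stands, and it limits the weight of the point. It does not supply the missing rule: caution in interpretation does not define a denominator, and the literal reading of the composite is not written into F10.

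**Conclusion.** The gap is real. F10 fixes neither the denominator nor the handling of a missing 6-month SRQ-20, and names no baseline adjustment for the SRQ-20 model. If the composite is coded missing whenever SRQ-20 is missing, known failures are dropped. Under the assumed rates, 7.5 points shrink to 2.3 (0.0 to 4.2 as q runs from 0% to 40%), with no shrinkage when retained and disengaged women are interviewed equally often.

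The shrinkage rests on three assumptions: that the default coding is used, that EFB works largely by improving retention, and that disengaged women are interviewed less often. Bias is therefore conditional, and for SRQ-20 alone its direction is unknown. For secondary outcomes of a feasibility pilot this should be corrected before analysis, but it does not threaten the primary aims.

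**What to change.** Add to F10:

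1. All 80 individually randomised women form the denominator for between-arm comparisons. The composite is a failure whenever the medical record shows no HIV visit in the last 30 days, whether or not SRQ-20 is available. State a convention for documented transfers, since visits elsewhere may not appear in the site record.
2. For women retained in care but without a 6-month SRQ-20, use multiple imputation from variables available in both arms: baseline SRQ-20, EPDS, site, arm and record-based retention. Do not use session-level SRQ-20, because ESC has no counselling sessions. Report missing-as-failure and best/worst-case bounds as sensitivity analyses only, since missing-as-failure can itself create a difference.
3. Adjust the 6-month SRQ-20 GLM for baseline SRQ-20.

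The cost is a few sentences and some extra analysis work. The variables are already collected. Composite rates will look lower than under a completers-only coding.
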